Urinalysis ^m	X					X	X
Urine pregnancy test ⁿ	X				X	X	X
ADA ^o	X					X	X
Efgartigimod administration ^p	X	X	X	X			
*Prior/concomitant therapy ^q	←-----X----->						
*Adverse events	←-----X----->						

ADA=anti-drug antibodies; EoS/ED=end of study/early discontinuation; ITPEV=intertreatment period visit in Part B; MG-ADL=Myasthenia Gravis Activities of Daily Living; TPEV=treatment period visit in Part B; Y=previous visit; UNS=unscheduled visit

[figure not shown]
^a The ITPE_nV_n occur every 90 ±7 days after Y. The visit denominator (“n”) will start at 1 at each period. At each ITPE_nV_n, an evaluation of the need for (re-) treatment should be done prior to decide whether assessments listed for ITPE_nV_n or TPE_nV1 are to be performed.

^b If a patient becomes eligible for (re-)treatment with efgartigimod but cannot complete the entire treatment period within the duration of the trial, the patient should continue to the EoS visit.

^c EoS will be up to a maximum of 3 years (1095±7 days) or until efgartigimod becomes commercially available or another option to access efgartigimod is available, whichever option comes first.

- ^d For patients who discontinue early from the trial, the assessments will depend on the visit at which it was decided that the patient had to discontinue (see Section 5.4). Patients who discontinue early from the trial within a treatment period should perform the planned assessments of the corresponding treatment period visit. These patients will not receive any further administration of efgartigimod during the trial and return for the ED visit 1 month (30 ±2 days) after the last dose administration. An unscheduled visit can be organized if deemed necessary by the investigator. Patients who discontinue early from the trial between the last visit of a treatment period (TPE_nV4) and the next intertreatment period visit (ITPE_nVn) should perform the ED assessments 1 month (30 ±2 days) after the last dose administration. Patients who discontinue early from the trial at the ITPE visit should perform the ED assessments instead of the ITPE_nVn assessments. Patients who discontinue prematurely from the trial after the ITPE visit should perform the ED assessments.
- ^e Before enrolling in ARGX-113-2002 from Part B, patients must first complete the early discontinuation (ED) visit assessments. The previous efgartigimod IV dose must have been received at least 30 days before entry into ARGX-113-2002.
- ^f An unscheduled (UNS) visit can occur at the request of the patient or the investigator. During the UNS visit, additional assessments as indicated in the SoA can be performed at the investigator's discretion, depending on the reason for the UNS visit.
- ^g The transition to Part B can be either ITPE0Vn or TPE1V1, depending on the patient status regarding the need for (re-)treatment upon transition from Part A. The first visit in Part B will always coincide with the EoA visit in Part A. The assessments done for the last visit in Part A should not be repeated in Part B.
- ^h Assessments of disease severity should be completed predose on dosing days and before any other trial-specific assessment, except weight, if applicable.
- ⁱ Weight will be measured at visit 1, the EoS/ED visit, and any visit when a weight change is obvious compared to the last weight measurement.
- ^j Vital signs (supine blood pressure, heart rate, body temperature) will be performed predose on dosing days. It is recommended that the method used to measure body temperature is maintained throughout the trial for each patient.
- ^k A 12-lead ECG will be recorded locally. The assessments on heart rate, PR, QT, and QRS intervals will be read centrally.
- ^l Samples for clinical laboratory tests (hematology, clinical chemistry) will be collected predose on dosing days, if applicable (see Appendix 3).
- ^m Urine samples will be collected predose on dosing days (see Appendix 3).
- ⁿ If a urine pregnancy test is carried out on a dosing day, then it should be performed predose (only for women of childbearing potential, see DEFINITION OF TERMS).
- ^o Samples for anti-drug antibodies (ADAs) will be collected predose on dosing days (if applicable) and collected only in the case of early discontinuation and not at the EoS visit.
- ^p Efgartigimod will be administered as an intravenous (IV) infusion over a period of 1 hour at visits 1, 2, 3, and 4 of each treatment period. Patients will remain at the site for at least 1 hour following the end of the infusion for safety monitoring based on the patient's clinical status. At TPE_nV1, the conditions for (re-)treatment will be checked before administration of efgartigimod.
- ^q All available vaccination history will be recorded as part of the participant's prior medication for vaccinations received in the past or concomitant medication for vaccinations received during the trial. For vaccines where multiple doses or boosters are received, only the most recent one must be recorded.
- * Assessments highlighted by use of bold italics indicate assessments that may be carried out as a telephone assessment visit under the conditions outlined in Appendix 8.

Figure 2: ARGX-113-1705 Trial Design for Part B

ED = Early Discontinuation; EoA = End of Part A; EoS = End of Study; ITPE_n V_n = Inter Treatment Period_(number) Visit in Part B; TPE_n B = Treatment Period_(number) Baseline in Part B; TPE_n = Treatment Period_(number) Visit_(number) in Part B
Patients will be dosed on an "as needed basis".

Note: All available vaccination history will be captured as part of the participant's prior medication for vaccinations received in the past or concomitant medication for vaccinations received during the trial as described in the General Schedule of Assessments for Part A (Table 1).

^a Weekly visits (window ±1 day) during the Treatment Periods

^b Visits every 90 days (window ±7 days) during the Inter Treatment Periods. The length between Treatment Periods may vary for each patient.

^c EoS visit (window ± 7 days)

^d D1095 or when efgartigimod becomes commercially available or another option to access efgartigimod is available, whichever option comes first

^e Patients enrolling in ARGX-113-2002 from Part B of ARGX-113-1705 must have received the previous dose of efgartigimod IV at least 30 days prior to entry into ARGX-113-2002 and must first complete the ED visit assessments from ARGX-113-1705.

TABLE OF CONTENTS

TITLE PAGE	1
SIGNATURE OF SPONSOR.....	3
SIGNATURE OF INVESTIGATOR	4
DOCUMENT HISTORY	5
SUMMARY OF CHANGES	5
SYNOPSIS 11	
LIST OF ABBREVIATIONS.....	30
DEFINITION OF TERMS	34
1. INTRODUCTION	37
1.1. Background Information.....	37
1.2. Investigational Medicinal Product.....	38
1.3. Standard of Care and Rationale for the Use of Efgartigimod.....	39
1.4. Benefit-Risk Assessment	40
2. TRIAL OBJECTIVES	43
2.1. Primary Objective	43
2.2. Secondary Objective	43
2.3. Tertiary Objectives	43
3. TRIAL ENDPOINTS	44
3.1. Primary Endpoint.....	44
3.2. Secondary Endpoint.....	44
3.3. Tertiary Endpoints	44
4. INVESTIGATIONAL PLAN.....	45
4.1. Summary of Trial Design	45
4.2. Discussion of Trial Design	49

FDA	Food and Drug Administration
FSH	follicle-stimulating hormone
GCP	good clinical practice
gMG	generalized myasthenia gravis
HBV	hepatitis B virus
HCV	hepatitis C virus
HEL-ABDEG™	full-length monoclonal antibody analog of ABDEG™
HIV	human immunodeficiency virus
IB	investigator's Brochure
ICF	informed consent form
ICH	International Council for Harmonisation
IEC	Independent Ethics Committee
IgG	immunoglobulin gamma
IMP	investigational medicinal product
IND	investigational new drug
IRB	Institutional Review Board
ITPV	intertreatment period visit in Part A
ITPEV	intertreatment period visit in Part B
IV	intravenous

IVIg	intravenous immunoglobulin
LRP4	lipoprotein receptor-related protein 4
MG	myasthenia gravis
MG-ADL	Myasthenia Gravis Activities of Daily Living
MGFA	Myasthenia Gravis Foundation of America
MuSK	muscle-specific kinase
NCI	National Cancer Institute
NSID	non-steroidal immunosuppressive drug
PD	pharmacodynamic(s)
PHQ-9	Patient Health Questionnaire item 9
PLEX	plasma exchange
PK	pharmacokinetic(s)
QMG	Quantitative Myasthenia Gravis
SAE	serious adverse event
SEB	study entry baseline
SoC	standard of care
SOP	standard operating procedures
SUSAR	suspected unexpected serious adverse reaction
TCB	treatment cycle baseline
TEAE	treatment-emergent adverse event
TPB	treatment period baseline
TPE	treatment period in Part B
TP _n B	subsequent treatment period baseline in Part A
TPE _n B	subsequent treatment period baseline in Part B

UNS	unscheduled visit
US	United States
WBC	white blood count
WHO(-DD)	World Health Organization (Drug Dictionary)

DEFINITION OF TERMS

Childbearing potential:	Women of childbearing potential are defined as all female participants unless they are postmenopausal (defined by continuous amenorrhea) for at least 2 years with a follicle-stimulating hormone (FSH) >40 IU/L or are surgically sterile (ie, who had a hysterectomy, bilateral oophorectomy, or have current documented tubal ligation or any other permanent female sterilization procedure).
Council for International Organizations of Medical Sciences (CIOMS):	
The Council for International Organizations of Medical Sciences (CIOMS) is an international, non-governmental, non-profit organization established jointly by World Health Organization (WHO) and UNESCO in 1949. They provide a set of ethical principles regarding human experimentations, including International Reporting of Adverse Drug Reactions and International Reporting of Periodic Drug-Safety Update Summaries.
 
The CIOMS form provides a standardized format for the reporting of suspected adverse reactions to any particular medical product and is the acceptable and widely used format for reporting suspect adverse drug reaction (ADR)/suspected unexpected serious adverse reaction (SUSAR) in clinical trials.

Contract Research Organization (CRO):	A person, or a group of persons (commercial, academic, or other), who as an independent contractor with argenx BVBA, assume(s) 1 or more obligations of argenx BVBA, eg, development of a protocol, selection and/or monitoring of investigators, evaluation of reports, preparation of materials to be submitted to Health Authorities.
Cycle	A cycle is a treatment period plus the intertreatment period.
Database Lock:	An action taken to prevent further changes to a trial database. A database is locked after review, query resolution, data cleaning and determination that it is ready for analysis.
Data Safety Monitoring Board (DSMB):	Independent group of experts that advises and whose responsibilities are to periodically review and evaluate the accumulated trial data for participant safety, trial conduct and progress and, when appropriate, efficacy and to make recommendation to the sponsor concerning the continuation, modification or termination of the trial.

Eligible:	Qualified for roll-over into the trial based upon strict adherence to inclusion/exclusion criteria.
Good Clinical Practice (GCP):	A standard for the design, conduct, performance, monitoring, auditing, recording, analyses, and reporting of clinical trials that provides assurance that the data and reported results are credible and accurate, and that the rights, integrity, and confidentiality of trial subjects are protected (ICH E6).
Institutional Review Board (IRB)/Independent Ethics Committee (IEC):	An independent body (a review board or a committee, institutional, regional, national, or supranational), constituted of medical professionals and non-medical members, whose responsibility it is to ensure the protection of the rights, safety and well-being of human subjects involved in a trial and to provide public assurance of that protection, by, among other things, reviewing and approving / providing favorable opinion on, the trial protocol, the suitability of the investigator(s), facilities, and the methods and material to be used in obtaining and documenting informed consent of the trial subjects.
Informed Consent/ Informed Consent Form (ICF):	A process by which a clinical investigation participant voluntarily confirms his or her willingness to participate in a particular clinical trial, after having been informed of all aspects of the trial that are relevant to the participant's decision to participate. Informed consent is documented by means of a dated and signed informed consent form (ICF).
International Conference on Harmonisation (ICH):	The International Conference on Harmonisation of Technical Requirements for Registration of Pharmaceuticals for Human Use (ICH) is a project that brings together the regulatory authorities of Europe, Japan and the United States and experts from the pharmaceutical industry in the 3 regions to discuss scientific and technical aspects of pharmaceutical product registration.
Investigational Medicinal Product:	A pharmaceutical form of an active ingredient being tested or used as a reference in a clinical trial, including a product with a marketing authorization when used in a way different from the approved form, or when used for an unapproved indication, or when used to gain further information about an approved use.
Protocol amendment:	A written description of a change(s) to or formal clarification of a protocol.

Treatment: Term used throughout the clinical trial to denote a set of investigational product(s) or marketed product(s) intended to be administered to a subject.

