- ^e An unscheduled (UNS) visit can occur at the request of the patient or the investigator. During the UNS visit, additional assessments as indicated in the SoA can be performed at the discretion of the investigator, depending on the reason for the UNS visit.
- ^f No trial-related assessment is to be carried out before the patient has signed the informed consent form (ICF).
- ^g Assessments of disease severity should be completed predose on dosing days and before any other trial-specific assessment, except for obtaining informed consent at SEB and the weight assessment, if applicable. The MG-ADL scale should be administered before the QMG scale. Acetylcholinesterase inhibitors must be halted for at least 12 hours before the QMG assessment (consistent with the revised manual for the QMG test as recommended by the Myasthenia Gravis Foundation of America [MGFA]).
- ^h Suicidal ideation and behavior will be assessed predose on dosing days via a targeted question based on the Patient Health Questionnaire item 9 (PHQ-9).
- ⁱ The physical examination will be performed predose on dosing days. See Section 7.2.3 for an overview of the different assessments.
- ^j Weight will be measured at SEB, at the EoA/ED visit, and when there is an obvious weight change compared to the last weight assessment. Height will be measured at SEB.
- ^k Vital signs (supine blood pressure, heart rate, body temperature) will be performed predose on dosing days. It is recommended that the method used to measure body temperature at SEB is maintained throughout the trial for each patient.
- ^l ECG will be performed predose on dosing days.
- ^m Samples for clinical laboratory tests (hematology, clinical chemistry) will be collected predose on dosing days (see Appendix 3). Patients need to have fasted at least 8 hours prior to each sampling.
- ⁿ Urine samples will be collected predose on dosing days (see Appendix 3).
- ^o A urine pregnancy test will be performed predose on dosing days on the urine samples taken for urinalysis (only for women of childbearing potential, see DEFINITION OF TERMS).
- ^p Samples for pharmacodynamic (PD) biomarkers will be collected predose on dosing days (see Appendix 3). Anti-AChR antibodies will be measured in AChR-Ab seropositive patients only. Anti-MuSK antibodies will be measured in MuSK-Ab seropositive patients only. Information on the AChR/MuSK-Ab serotype (seronegative or seropositive) is available from trial ARGX-113-1704.

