5.1. Informed Consent and Roll-Over Visit

The roll-over visit (SEB) can be either ITP₀V₁ or TP₁V₁, depending on the patient status regarding the need for (re-)treatment upon roll-over from trial ARGX-113-1704. The first visit in trial ARGX-113-1705 will always coincide with the last visit in trial ARGX-113-1704.

The patient must sign the informed consent form (ICF) prior to any trial-related assessment. The assessments done for the last visit in trial ARGX-113-1704 should not be repeated.

Prior to signing the ICF, trial patients will be instructed not to participate in any other clinical trial that involves an intervention or collection of data until the completion of the current trial.

After informed consent has been obtained, participants of trial ARGX-113-1704 will be screened at the site for eligibility to roll over to this trial based on the inclusion and exclusion criteria defined in Sections 4.3.1 and 4.3.2, respectively.

In addition to obtaining written informed consent and the eligibility check, the following assessments will be performed at SEB:

- Clinically relevant medical and surgical history, clinically relevant prior treatments and all concomitant medications (see Sections 6.8 and 7.2.5)
- Demographic characteristics (date of birth, sex, race, and ethnicity, per national regulations)
- Assessments of disease severity – the MG-ADL scale should be administered before the QMG scale
- Suicidal ideation and behavior will be assessed via a targeted question based on the Patient Health Questionnaire item 9 (PHQ-9)¹⁷
- Complete physical examination, including at a minimum: general appearance, skin, lymph nodes, musculoskeletal/extremities, abdomen, cardiovascular, respiratory, and neurological systems
- Weight and height
- Vital signs (supine blood pressure, heart rate, body temperature). It is recommended that the method used to measure body temperature at SEB is maintained throughout the trial for each patient
- ECG (heart rate, PR, QT, and QRS interval)
- Clinical laboratory tests (see Appendix 3 for an overview of the clinical laboratory tests that will be assessed). Patients need to have fasted at least 8 hours prior to sampling
- Urinalysis
- Urine pregnancy test (only for women of childbearing potential, see DEFINITION OF TERMS)

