7.2.1.5. Reporting and Follow-up Requirements for Pregnancies

7.2.1.5.1. Pregnancies in Female Patients

Urine pregnancy tests will be conducted and analyzed locally at visits as detailed in the General Schedule of Assessments for Part A (Table 1) and for Part B (Table 2). Results will be recorded in the eCRF.

If a patient becomes pregnant after the administration of efgartigimod and up to 90 days after the patient received the last infusion, the sponsor and/or sponsor's designee should be informed immediately (ie, within 24 hours of the trial site's knowledge of the event). The following actions will be performed:

- The patient should immediately be discontinued from trial treatment.
- The patient should have the planned ED assessments.
- All planned assessments (see Sections 4.4 and 5.4) must be performed unless contraindicated by pregnancy (harmful to fetus) or unless the patient withdraws informed consent.

The investigator must update the patient with information currently known about potential risks and about available treatment alternatives. The pregnancy should be followed up to determine outcome, including spontaneous or voluntary termination, details of the birth, and the presence or

absence of any birth defects, congenital abnormalities, or maternal and/or newborn complications.

If required by local regulations, the female participant will be requested to sign a separate pregnancy ICF. Full details will be recorded on a paper Pregnancy Report Form and submitted via email or fax (see the [Safety Mailbox/Fax](#) details on the title page of this protocol), and reporting details will be specified in the trial manual. The investigator will update the Pregnancy Report Form with additional information as soon as the outcome of the pregnancy is known.

If the outcome of the pregnancy is an SAE, then this must be additionally reported as an SAE on the appropriate SAE Report Form.

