7.2.2. Clinical Laboratory Evaluations

In Part A, blood and urine samples for determination of clinical chemistry, hematology and urinalysis will be analyzed at a central laboratory. PD and ADA will be analyzed at a specialty laboratory as indicated in the General Schedule of Assessments for Part A ([Table 1](#)) and [Appendix 3](#). Patients need to be fasting for at least 8 hours prior to the sampling for clinical laboratory tests as from SEB up to EoA.

In Part B, blood and urine samples for determination of clinical chemistry, hematology and urinalysis will be analyzed at local laboratories and results will not be recorded in the eCRF. Blood samples for ADA will be analyzed at a specialty laboratory as indicated in the General Schedule of Assessments for Part B ([Table 2](#)) and [Appendix 3](#).

Additional safety samples may be collected if clinically indicated at the discretion of the investigator.

For all patients of childbearing potential, a urine pregnancy test will be conducted and analyzed locally at the site (on the urine samples taken for urinalysis, if applicable) at all visits in Part A ([Table 1](#)) and at visit 1 and 4 of each Treatment Period, at ITPE visits, at EoS/ED and at the discretion of the investigator in Part B ([Table 2](#)).

The estimated total maximum blood volume needed for a patient during Part A of the trial (when completing the trial up until the last visit) is between 170 mL for a patient who receives 1 Treatment Period only and 362 mL for a patient who receives a maximum of 6 Treatment Periods. The estimated total maximum blood volume needed for a patient during Part B of the trial (when completing the trial up until the last visit) is between 24 mL for a patient who receives 1 Treatment Period only and 100 mL for a patient who receives 6 Treatment Periods.

Clinical laboratory tests will be reviewed for results of potential clinical significance at all time points throughout the trial. The investigator will evaluate any change in laboratory values. If the investigator determines a laboratory abnormality to be clinically significant, it will be considered as a laboratory AE; however, if the abnormal laboratory value is consistent with a current diagnosis, it may be documented accordingly without being reported as an AE.

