APPENDIX 9: Contraceptive and Barrier Guidance

Definitions

Woman of childbearing potential

A woman is considered to be of childbearing potential unless she is either:

- a. Postmenopausal: A postmenopausal state is defined by continuous amenorrhea for at least 1 year without an alternative medical cause with a follicle-stimulating hormone (FSH) measurement of >40 IU/L. A historical pretreatment FSH measurement of >40 IU/L is accepted as proof of a postmenopausal state for women on hormone replacement therapy
- b. Surgically sterilized: Women who have had a documented permanent sterilization procedure (ie, hysterectomy, bilateral salpingectomy, or bilateral oophorectomy)

Contraception Guidance

Female Contraception for Women of Childbearing Potential

Women of childbearing potential must use a highly effective or acceptable method of contraception which should be maintained at minimum until 90 days after last dose of IMP.

The following methods are considered highly effective methods of contraception:

1. Combined (estrogen and progestogen containing) hormonal contraception associated with inhibition of ovulation
 - Oral
 - Intravaginal
 - Transdermal
2. Progestogen-only hormonal contraception associated with inhibition of ovulation
 - Oral
 - Injectable
 - Implantable

3. Intrauterine device (IUD)
4. Intrauterine hormone-releasing system (IUS)
5. Bilateral tubal occlusion
6. Vasectomized partner
7. Sexual abstinence

The following methods are considered acceptable methods of contraception:

1. Progestogen-only oral hormonal contraception in which inhibition of ovulation is not the primary mode of action
 - a. Oral
 - b. Injectable
 - c. Implantable
2. Male or female condom with or without spermicide
3. Cap, diaphragm, or sponge with spermicide

Male Contraception

An acceptable method of contraception is a condom.

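### Non-sterile women with at least 2 years of amenorrhea from another medical cause and FSH >40 IU/L must use contraception under Appendix 9 but, on the literal wording, have no scheduled pregnancy test

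*Protocol*

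**What the plan says.** Protocol Definition of Terms counts every female participant as of childbearing potential unless she is surgically sterile or "postmenopausal (defined by continuous amenorrhea) for at least 2 years with a follicle-stimulating hormone (FSH) >40 IU/L".

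Protocol Appendix 9 gives its own definition. Its postmenopausal exemption requires "continuous amenorrhea for at least 1 year without an alternative medical cause", also with FSH above 40 IU/L. The contraception duty sits there: "Women of childbearing potential must use a highly effective or acceptable method of contraception", until at least 90 days after the last dose.

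Testing is tied to the first definition. Table 1 footnote o (Part A) and Table 2 footnote n (Part B) both limit the test with the words "only for women of childbearing potential, see DEFINITION OF TERMS". Section 5.1 repeats this for the roll-over visit: "Urine pregnancy test (only for women of childbearing potential, see DEFINITION OF TERMS". Sections 5.2 to 5.4 do the same for later visits, and exclusion criterion 2 cites Definition of Terms for the negative test required at study entry.

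Two other sections mention testing. Section 7.2.2 says: "For all patients of childbearing potential, a urine pregnancy test will be conducted and analyzed locally at the site", then cites Tables 1 and 2 for the visits. Section 7.2.1.5.1 says: "Urine pregnancy tests will be conducted and analyzed locally at visits as detailed in the General Schedule of Assessments". Neither gives a definition of its own.

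**The concern.** The two definitions serve different purposes and do not agree. A woman can be treated as able to conceive by the contraception rule and as unable to conceive by the testing rule.

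Section 1.4 says that safety in pregnancy has not been established and that the drug should not be given to pregnant women. Section 4.4 makes pregnancy a mandatory reason to leave the trial, and section 7.2.1.5.1 adds: "The patient should immediately be discontinued from trial treatment". The scheduled urine test is the routine check that would set those steps in motion. For a woman in the gap it is missing, and nothing else in the schedule prompts a test in someone recorded as not of childbearing potential.

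**Working it through.** The plan gives no count of pregnancy tests, so there is no stated figure to reproduce. The check sets the definitions side by side and then counts scheduled tests in stated scenarios.

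**Definitions**

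| | Definition of Terms | Appendix 9 |
|---|---|---|
| Minimum amenorrhea | 2 years | 1 year |
| FSH | >40 IU/L | >40 IU/L |
| Condition on cause | none | no other medical cause |
| Hysterectomy or bilateral oophorectomy | exempt | exempt |
| Rule it governs | pregnancy tests | contraception |

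Applied to particular women:

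- **Not surgically sterile, at least 2 years of amenorrhea from another medical cause, FSH >40.** Exempt under Definition of Terms, so no scheduled test. Not exempt under Appendix 9, so contraception is required. This is the gap.
- **Same history, but the cause is hysterectomy or bilateral oophorectomy.** Exempt under both. No conflict.
- **FSH 40 or below, no FSH result, or less than 2 years of amenorrhea, and not surgically sterile.** Not exempt under Definition of Terms, so tested.
- **1 to under 2 years of amenorrhea, no other cause, FSH >40.** Tested under Definition of Terms, exempt from contraception under Appendix 9. This is the reverse mismatch and bears on the choice of fix.

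**Scheduled tests in one illustrative course**

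Inputs: visit days from Table 1, Table 2 and section 7.2.2, at nominal days without windows. One treatment period starts on day 1 of Part A (the roll-over visit is its visit 1), and one starts at the end-of-Part-A visit.

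- Part A, treatment visits on days 1, 8, 15 and 22: 4.
- Part A, intertreatment visits on day 22 + 30k for k = 1 to 10, days 52 to 322: 10. The next would be day 352, which is 365 − 352 = 13 days before the end-of-Part-A visit, so that visit replaces it.
- Part A, end visit on day 365: 1. **Total 4 + 10 + 1 = 15.**
- Part B, visit 1 coincides with day 365 and is already counted. Visit 4 on day 365 + 21 = 386: 1.
- Part B, intertreatment visits on day 386 + 90k for k = 1 to 7, days 476 to 1016: 7. The next, day 1106, falls after day 1095.
- Part B, end of study on day 1095: 1. **Total 1 + 7 + 1 = 9.**
- Both parts: 15 + 9 = 24.

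In this course a tested woman has a same-day test at all 4 Part A infusions and at visits 1 and 4 of the Part B period, so at 6 of 8 infusions. The woman in the gap has one at 0 of 8.

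**How far the count moves, Part A alone**

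- No treatment period: days 1, 31, …, 331 give 12 tests; day 361 is replaced by the end visit, which adds 1. Total 13.
- Six back-to-back periods (section 7.2.2 plans blood volume for up to 6), starting on days 1, 52, 103, 154, 205 and 256: 6 × 4 = 24 treatment visits, intertreatment visits on days 307 and 337, and the end visit. Total 24 + 2 + 1 = 27.

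**The case against.** **The word itself.** A site could read postmenopausal as already ruling out other causes, and so would test this woman. That is a sensible clinical reading. But the parenthesis in Definition of Terms defines the word by amenorrhea alone, and Appendix 9 found it necessary to state the cause condition. The gap therefore rests on the literal wording; the documents do not show that any site applied it that way. SAP section 3.3.1 lists a single childbearing-potential item, so a split classification of one woman cannot be seen in the data plan.

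**Section 7.2.2.** It names patients of childbearing potential without pointing to Definition of Terms, and its table references could be read as giving timing only. It offers no definition, however, and the tables it cites carry footnotes that lead back to Definition of Terms. It does not settle the matter.

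**Existing safeguards.** Tests can be done at unscheduled visits and, in Part B, at the investigator's discretion. The bar on dosing in pregnancy and the discontinuation rules apply to any pregnant patient, however classified. All of this stands; what is missing is the scheduled check.

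**Timing.** The SAP is for the final analysis, is dated 20 September 2022 and describes much of the conduct in the past tense. Remaining exposure may be short, although the documents do not say that dosing has ended.

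**Stronger readings.** A reader might infer that every woman with amenorrhea from another medical cause goes untested. That is wrong for those who are surgically sterile by both definitions, where no conflict arises, and for those who fail the 2-year or FSH condition, who are tested. A reader might also take 15 to 24 missed tests as a range. It is not: Part A alone can give 13 or 27.

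**Conclusion.** The inconsistency is real in current protocol text, but narrow. It affects women who are not surgically sterile, have at least 2 years of continuous amenorrhea from another medical cause, and have FSH above 40 IU/L. They owe contraception under Appendix 9 and, read literally, have no scheduled urine pregnancy test in either part.

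How many such women there are cannot be derived. It may be none, and it cannot exceed the women among at most 167 patients (SAP section 1.3). The 15 and 9 missed tests describe one assumed course, with one treatment period per part and the full 1,095 days; as-needed treatment and an earlier end of Part B would change them.

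This is a participant-safety matter only. A reader might infer that the safety results are affected or that a pregnant woman was dosed. The documents support neither: no endpoint, analysis set or summary depends on this definition, and no such case is described. A small correction is worth considering.

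**What to change.** In Definition of Terms, extend the parenthesis so that amenorrhea counts only when it has no other medical cause, using the condition already in Appendix 9. Leave the 2-year threshold, the FSH limit and the sterilization wording as they are. Replacing the definition with Appendix 9's would bring in the 1-year threshold and take tests away from women with 1 to under 2 years of amenorrhea who are tested now. Keeping 2 years means that no woman loses a test.

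For any woman still being dosed who was classed as not of childbearing potential on amenorrhea and FSH, check the recorded cause once. Start scheduled tests if another cause is found. Medical history is already collected at study entry (section 7.2.5), and no new FSH measurement is needed.

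At the same time, correct the pointers from exclusion criterion 2 to Appendix 9. The Synopsis prints a field error, and section 4.3.2 names Appendix 8 and inserts its COVID-19 text before reaching Appendix 9. This part is clerical.

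Cost: a small amendment needing the approvals in section 4.5 and carried into the country-specific versions, one records check, and a few local urine tests for any woman reclassified. The two definitions would still differ on the 1-year versus 2-year threshold and on sterilization procedures.
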